#### 9.5 Study Design:

Describe study design in one to two sentences (e.g., prospective, use of existing records/data /specimens, observational, cross-sectional, interventional, randomized, placebo-controlled, cohort, etc.). Specify the phase – Phase I, II, III, or IV – for FDA-regulated investigational drug research

The study design is a 1:1 randomized, double-blind, placebo-controlled, parallel trial. The ongoing assessment and monitoring of subjects enrolled in the study will be conducted by a Masters-level Clinical Research Psychologist under the supervision of a credentialed provider within the WRNMMV Behavioral

Weight/ Height	X		X								X	Yes
Psychiatric examination	X										X	Yes
Physical examination	X										X	Yes
Chemistry panel and CBC w/dif	X										X	Yes
Thyroid function, HIV, HCG, hepatitis screen and urine drug screen	X										X	Yes
Liver function panel	X		X	X	X	X	X	X	X	X	X	Yes
Menstrual history (women)	X											Yes
Family History Screen	X											Yes
SCID-IV-TR	X											
Placebo lead-in												
Study drug/ Placebo			X	X	X	X	X	X	X	X	X	
Efficacy Measures												
CAPS	X		X					X			X	
CGI,	X		X	X	X	X	X	X	X	X	X	
MADRS	X		X	X	X	X	X	X	X	X	X	
HAM-A			X					X			X	
SDS			X					X			X	
PCL-C			X	X	X	X	X	X	X	X	X	
UKU-SERS-Pat	X		X	X	X	X	X	X	X	X	X	
LSAS			X					X			X	
PSQI, DES			X					X			X	
WHOQOL BREF, CD-RISC			X					X			X	
CTQ			X									
SCL-90			X					X			X	
PDI	X											

Description of Data	Scr	Stabil	V1	V2	V3	V4	V5	V6	V7	V8	V9 a	SOC
Week			0	1	2	3	4	5	6	7	8	
Safety Measures												
Adverse events	X	X	X	X	X	X	X	X	X	X	X	
MRS			X							X		

**Abbreviations:** Sc = Screening Visit; Sta = Stabilization Visit; CAPS = Clinician-Administered PTSD scale; CD-RISC = Connor-Davidson Resilience Scale; CGI = clinical global impression scale; CTQ = Childhood Trauma Questionnaire; DES = Dissociative Experience Scale; F/U = Follow-up visit; HAM-A = Hamilton Anxiety Rating Scale; HCG = blood pregnancy test; Hollingshead = Hollingshead 4 Factors of Social Status Scale; LSAS = Liebowitz Social Anxiety Scale; MADRS = Montgomery Depression Rating Scale;; PLC-C = PTSD Checklist; UKU-SERS-Pat = UKU Side Effect Rating Scale, Self rating version; PDI = Peri Traumatic Distress Inventory; PSQI = Pittsburgh Sleep Quality Index; SCID-IV-TR = Structure Clinical Interview for DSM-IV; SCR = screen; SCL-90 = Symptom Checklist, 90 items; SDS = Sheehan Disability Scale; WHOQOL BREF = World Health Organization Quality of Life WO = washout phase.

aExit visit to be performed at Visit 9 or sooner if the patient is discontinued from the study.

WO = washout phase. May vary depending on drug but in general is 51/2 lives. If the subject is medication free, they may proceed to Study Period I.

bVisits during Study Period II may happen within 2 days of the scheduled visit. SCO = Standard of Care activity - Affirmative notation; Default notation is left blank indicating an activity that is research-related.

The 10-week clinical study will be conducted in two phases, a minimum of 2-weeks and maximum of 4-weeks screening and stabilization phase (Phase I) and an 8-week double-blind placebo controlled treatment (Phase II).

In Phase I, indicated as the "Screening Period" in **Figure 1 Riluzole Augmentation for PTSD**, patients who are suboptimal responders (see inclusion/exclusion criteria) to other psychotropic drugs will continue these at stable dosage for at least 2 weeks prior to study randomization (dose stabilization). Use of antidepressant and sedative/hypnotic drugs at stable dose is permitted. Subjects will be contacted by phone after 1 week to assure that no medication changes were made and to schedule the first Phase II visit.

Subjects will also complete the screening visit where they will be evaluated for study entry and enrollment. Psychiatric history and diagnosis will be administered by study staff at each site using the SCID-P (First et al., 1995) and the DSM-IV Diagnostic Criteria (American Psychiatric Association, 1994). Patients who meet DSM-IV criteria for PTSD must have a Clinician Administered PTSD Scale (CAPS) of 40 at Visits 1 and 2 to be included in the study. Those entering the study at the completion of a referring INTRuST or other medication trial for PTSD will also receive a CGI assessment, and must have a score indicating "NOT improved" or "NOT very much improved" on the CGI scale at the completion of their medication trial to be eligible. The screening visit will include the screening tests, patient history, and psychiatric and physical examinations, as well as menstrual history in females. Subjects will undergo a physical exam, supine and standing vital signs, complete blood cell counts (CBC) with differential, electrolytes, thyroid function test, liver function tests, fasting blood sugar, hematology profile, urinalysis (including screens for substances of abuse), hepatitis screen, SCID, and CAPS. Women of childbearing capacity will have a baseline serum  $\beta$ -HCG. A positive  $\beta$ -HCG will exclude them from participating in the study. Subjects must also have a negative Human Immunodeficiency Virus (HIV) test. Results of these tests will identify patients who should be excluded because of active medical problems or substance abuse that might affect the clinical phenomenology or treatment response and to identify conditions that might make randomization into one of the treatment arms less safe. The CGI will be used to collect information on overall improvement, and the UKU side effect rating scale will be used to collect information on side effects. Finally, eligible subjects who consent to participate in the baseline  $^1\text{H}$  MRS portion of the study will undergo the scan during the screening visit.

The time commitment for the telephone confirmation is estimated to be 10 minutes. The screening visit will take 4 hours. The time commitment for the baseline  $^1\text{H}$  MRS scan is estimated to be 60-90 minutes.

Phase II, indicated as the "Acute Double-Blind Period", in **Figure 1 Riluzole Augmentation for PTSD**, begins after the completion of the stabilization phase, where subjects will be randomized at a ratio of 1:1 to receive an 8-week double-blind treatment of either riluzole or placebo. Riluzole or placebo will be administered in two divided doses (two tablets twice a day). During the clinical trial, all blinded study medication will be manufactured to identical appearance. All members of the research team and treatment staff will be blinded. Subjects will be assessed weekly from Visit 1 through Visit 9 (see Schedule of Events, **Section 5.5.8 Study Time Line**). Riluzole therapy will be initiated at a dose of 50mg twice daily, as will matching placebo for those subjects randomized to placebo. Riluzole may be increased to 200 mg/day thereafter if the subject's weekly case history (subject self-reported symptomatology and CAPS score and/or additional psychological clinical battery diagnostics) indicate that the increased dose may have therapeutic benefit. The maximal allowable dose of riluzole permitted is 200 mg/day. The minimal allowable dose of riluzole permitted is 100 mg/day. Those subjects unable to tolerate the lowest allowable dose will be discontinued from the study. Eligible subjects who consented to participate in the baseline  $^1\text{H}$  MRS portion of the study will undergo a post-treatment scan between visits 8 and 9.

The time commitment for the weekly scheduled visit is estimated to be 2-4 hours. The time commitment for the post-treatment  $^1\text{H}$  MRS scan is estimated to be 60 to 90 minutes.

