## 11.2 Sample Size Estimation:

A power analysis confirms the study will be able to detect a 9 point change in CAPS score in subjects receiving riluzole augmentation versus placebo using a sample size of 50, assuming a two-tailed test, an  $\alpha = 0.05$ , and a standard deviation of 15 (based on the PI's experience in this population seeking treatment at WRNMMC). This yields a power of 0.844. Power increases to 0.909, under the same assumptions, when a single-tailed test is used. The difference value of 9 is considered the minimally clinically significant difference and is supported by recent publications (Krystal et al, 2013; Schnurr et al, 2001; Weathers et al, 2001; Fontana et al, 1997; Norman et al, 2003; Lunney et al, 2007).

The SAS System  
 The POWER Procedure  
 Two-Sample t Test for Mean Difference  
 Fixed Scenario Elements  
 Distribution Normal  
 Method Exact  
 Number of Sides 2  
 Mean Difference 9  
 Standard Deviation 15  
 Group 1 Sample Size 50  
 Group 2 Sample Size 50  
 Null Difference 0  
 Alpha 0.05

Computed Power  
 Power 0.844

The SAS System  
 The POWER Procedure  
 Two-Sample t Test for Mean Difference  
 Fixed Scenario Elements  
 Distribution Normal  
 Method Exact  
 Number of Sides 1  
 Mean Difference 9  
 Standard Deviation 15  
 Group 1 Sample Size 50  
 Group 2 Sample Size 50  
 Null Difference 0  
 Alpha 0.05

Computed Power  
 Power 0.909

To allow for ineligibility (30-40%) and the possibility that more participants will be needed from

WRNMMC (~2:1 ratio), a total of up to 158 participants will be consented study-wide, with up to 104 participants recruited at WRNMMC.

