## 12.6 Exclusion Criteria:

Order Number	Criteria
	
b. Exclusion Criteria - Subjects will be excluded from the study for any of the following reasons:
 
 
1. Female subjects of childbearing capacity who test positively for <math>\beta</math>-HCG, or are either self-reporting as pregnant, planning to become pregnant, or nursing.
 
2. Presence of psychotic features.
 
3. Unable to provide informed consent or comply with study procedures.
 
4. Previous treatment with riluzole.
 
5. Serious, unstable illnesses including hepatic, renal, gastroenterological, respiratory, cardiovascular (including ischemic heart disease), endocrinologic, neurologic, immunologic, hematologic disease, or HIV. This includes individuals with a history of COPD by diagnosis as well as persons taking inhalers for Asthma or Reactive Airway Disease.
 
6. Clinically significant abnormal levels (3x ULN or greater) of serum transaminases (ALT/SGPT; AST/SGOT), current or past blood dyscrasia.
 
7. Subjects with uncorrected hypothyroidism or hyperthyroidism.
 
8. DSM-IV alcohol or substance abuse or dependence within 90 days of the screening visit.
 
9. Treatment with a reversible MAOI, guanethidine, or guanadrel within 1 week, or any change in fluoxetine dosing within 8 weeks prior to visit 2. Use of antidepressant and sedative/hypnotic drugs at stable dose is permitted.
 
10. Documented history of hypersensitivity or intolerance to riluzole.
 
11. Subjects with a current or past history of other axis I disorders including schizophrenia, schizoaffective disorder, bipolar disorder or dementia. However, those with a co-morbid history of other Axis I disorder like major depression, dysthymia or other anxiety disorders will be included; the justification for this is that approximately 70% of subjects with PTSD have co-morbid depression and or alcohol abuse, and restricting the sample to PTSD patients without depression will not accurately reflect the scope of this disorder.
 
12. Patients who are currently at high risk for homicide or suicide, as indicated by an affirmative answer to the question: "In the last three months, have you attempted to kill yourself, made specific plans to kill yourself, or had the intention to kill yourself?"
 
13. Current or planned litigation regarding the traumatic event.
 
14. Patients who recently started trauma focused cognitive behavioral psychotherapy (Patient's underlying educational or supportive individual or group therapy will be included).
 
15. Patient's actively enrolled in an evidence based psychotherapy treatment (e.g., Cognitive Processing Therapy or Prolonged Exposure Therapy) will be excluded until that therapy has concluded, but may be re-approached at that time if patient self-report or clinician referral suggests persistent PTSD symptoms upon conclusion of that treatment.
 
16. Subjects with an artificial cardiac pacemaker or metallic implants within their body will be enrolled at WRNMMC for the placebo-control clinical trial portion of the study only. These individuals, due to their pre-existing medical condition, are medically ineligible to participate in the <math>^1\text{H}</math> MRS imaging portion of the study. Further, the Magnetic Resonance (MRI) Screening Form is use at WRNMMC will be used for participant screening prior to any imaging procedures.
 
17. Use of benzodiazepines.
 

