**‘WOULD YOU LIKE TO BE IN THE STUDY?’ ”**

Referral information for alcohol/substance/sedative use and legal counseling in use at WRNMMC will be maintained in the clinical area where screenings are conducted. These are commonly posted and displayed for any individual to review. In general, these materials are also maintained with other health and welfare referrals so anonymity and privacy is maintained. As the participant leaves, the research clinician will inform the participant that resources are available should they be interested. If the research clinician feels the individual is at personal risk, active intervention will be necessary as detailed in Section 6.3. a.

Exclusion of acute or unstable medical illnesses: This would prevent subjects from tolerating the acute trial target doses of medication. We will include subjects with chronic stable medical illnesses.

Exclusion of women who are pregnant, plan to become pregnant or are breast-feeding : The study medication is a Category C drug, and we cannot be certain that it will not have teratogenic effects and it may be present in breast milk. As such, the Consent Form advises female participants to avoid becoming pregnant for at least one month after last receiving the study drug. Pregnancy within this time after the study drug is given may be a risk to an unborn baby. No evidence of teratogenic effects is found in the literature for males; however, all participants will be advised of the pregnancy category of the drug (C) and be informed that they should avoid attempting to conceive during participation or for at least one month after last receiving the study drug. Female participants will be given a pregnancy test post-treatment.

Because it is unknown whether riluzole can adversely affect human sperm, male participants will be informed of the possible risk to a child conceived while using the study drug and be advised they avoid engaging in sexual activity with the intent to conceive.

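### The only pregnancy test before dosing in the supplied plan is at Screening, so a negative result can be up to about four weeks old at first dose.

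*Combined protocol and SAP*

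**What the plan says.** The schedule of events in section 9.5 groups the pregnancy test with other laboratory screens: "Thyroid function, HIV, HCG, hepatitis screen and urine drug screen". Read against the column headings, that row is marked at Screening and at Visit 9, which doubles as the exit visit for anyone who stops early. The row "Liver function panel" is marked at Screening and at every visit from 1 to 9. Study drug is marked from Visit 1 (week 0) onward.

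The text agrees with the table. The screening-visit paragraph of section 9.5 says "Women of childbearing capacity will have a baseline serum" HCG, section 13.2 repeats this in its own Screening Visit paragraph, and the rationale under section 12.6 adds one post-treatment pregnancy test.

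The period before dosing is described as "a minimum of 2-weeks and maximum of 4-weeks screening and stabilization phase (Phase I"). The contact described within it is a telephone call: "Subjects will be contacted by phone after 1 week to assure that no medication changes were made" and to book the first Phase II visit.

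Exclusion criterion 1 removes women with a positive HCG, "or are either self-reporting as pregnant, planning to become pregnant, or nursing". On the drug itself, the rationale says "we cannot be certain that it will not have teratogenic effects".

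**The concern.** Pregnancy is an absolute exclusion, but a pregnancy test describes only the day on which it is drawn. Here the test is drawn in Phase I and the drug starts after Phase I, with no test between. A woman who conceives in that interval and does not know it would still be treated as HCG-negative at first dose.

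Two checks before dosing are described: confirmation that liver function tests are normal (section 14.2 a) and compilation of a medication list (section 13.2). Neither covers pregnancy. At stake is early fetal exposure to a drug for which the plan itself cannot exclude teratogenicity. This is a participant-safety point. It has no bearing on power, error rates or the estimate of effect.

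**Working it through.** No power or error-rate formula applies. The check is one of timing, followed by the cost of the remedy.

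**Inputs**

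- HCG marks: Screening and Visit 9 or exit (section 9.5 schedule).
- Liver panel marks: Screening and Visits 1 to 9 (same table).
- First dose: Visit 1, week 0 (same table, and the Phase II description in section 9.5).
- Phase I length: 2 to 4 weeks (section 9.5).
- Visit window in Study Period II: within 2 days (section 9.5 footnote).
- Number consented: up to 158, with 30–40% ineligible (section 11.2).

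**Age of the negative test at first dose**

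The age equals the time from the Screening draw to Visit 1.

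- If Screening is on day 1 of Phase I: 2 × 7 = 14 days at the least, 4 × 7 = 28 days at the most.
- If the 2-day window is also applied to Visit 1: 28 + 2 = 30 days.
- The documents do not fix Screening to day 1. If it falls later, the age is smaller and could be under 14 days.

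The supportable statement is therefore up to about 28 days.

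**Time on drug before the next scheduled test**

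Visit 1 is week 0 and Visit 9 is week 8, so a completer has 8 weeks of dosing. The two HCG tests are then 2 + 8 = 10 to 4 + 8 = 12 weeks apart.

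**Is the blank at Visit 1 a table-reading artefact?**

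The HCG and liver rows each split into 13 cells, matching the 13 headings. The liver row fills Visit 1 and the HCG row does not. The text in sections 9.5 and 13.2 places the single baseline HCG in the screening visit, so the word baseline cannot reasonably be read as Visit 1.

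**Number of extra tests**

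- Randomised: 158 × 0.60 = 94.8 to 158 × 0.70 = 110.6, or about 95 to 111.
- The share who are women of childbearing capacity is not given. Assuming 10% to 30%: 94.8 × 0.10 = 9.5 and 110.6 × 0.30 = 33.2, or about 9 to 33 tests.

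The number of exposed pregnancies cannot be calculated, because the documents give no count of women, contraceptive use or conception rate.

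**The case against.** The strongest objection is that the record is incomplete. Section 13.4, on eligibility assessment, only points to a Legacy Protocol, and section 15.1 does the same. The package insert mentioned in section 18.4 was not available, and the upper rows of the schedule are missing. A recheck before dosing could sit in any of these. This stands as a limit on certainty. It does not remove the point, because the HCG row is complete and a test held only elsewhere would still need to appear in the schedule.

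Four weeks is also the maximum. The study is called a 10-week study, and section 14.1 speaks of a 10-week delay to other treatment, so about 2 weeks may be usual. That stands too, but the plan permits 4.

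Other safeguards exist. Women who report pregnancy or plan it are excluded, participants are told not to try to conceive, adverse events are recorded at Stabilization, and there are weekly visits during dosing at which a pregnancy might be suspected. These reduce the group at risk and may shorten an exposure. None is a test, and none would reliably detect an unrecognised conception in Phase I.

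Finally, a Visit 1 test would miss a conception in the days just before it, and would leave the 8 weeks of dosing without a scheduled test. Both are true. The remedy deals with the Phase I gap only.

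**Conclusion.** The concern holds. On the supplied documents, the negative pregnancy test can be up to about 28 days old at first dose, and up to 8 weeks of dosing can follow before the next scheduled test. The 28-day figure assumes that Screening falls at the start of a 4-week Phase I. The 8-week figure assumes a completer in whom pregnancy is not suspected earlier. The expected number of exposed pregnancies is unknown and may be small. The change is still worth making, because the plan treats pregnancy as an absolute exclusion and the gap is cheap to close.

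**What to change.** Mark HCG at Visit 1 in the schedule for women of childbearing capacity, drawn with the Visit 1 liver panel. In section 14.2 a, add a negative result to the liver-function confirmation as a condition for starting study drug, and make the matching edits in sections 9.5 and 13.2. If the Legacy Protocol already requires such a test, carry it into the schedule.

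The age of the negative result at first dose then falls to the time needed to get the result back. The cost is one test per randomised woman of childbearing capacity, about 9 to 33 under the assumed 10% to 30% share, with no new visit or venepuncture. The downside is a small laboratory cost and possibly a short wait before the first dose. That wait may be new, since the liver confirmation could be met from the Screening sample. A rapid test at Visit 1, or a draw shortly before it, would limit the delay.

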An 8-week open-label study with riluzole in treatment-resistant DSM-IV bipolar depression (Protocol #03-M-00092) (Zarate et al., 2005). Eight subjects (57%) completed the 8-week trial. The reasons for discontinuation were adverse events (N =3; 2 asymptomatic increase in liver function tests, 1 renal calculi) and lack of improvement (N =3). Patients received riluzole at a mean daily dose of 171.4 + 42.6 mg (79% took a dose of 150 mg/day or more). The most common adverse events during the trial were fatigue (N = 4), decreased salivation (N = 4), reduced sleep (N = 4), nausea (N = 3), diarrhea (N = 3), weight loss (N = 3), decreased sex drive (N = 3), blurred vision (N = 3), and headache (N = 3). No serious adverse events were noted. Two subjects were discontinued from the study because of increased liver function tests (LFTs) that were more than three times the upper normal limit. These subjects were asymptomatic for hepatic dysfunction, and LFTs normalized shortly after discontinuing riluzole. One additional subject was discontinued because of renal calculi. Overall riluzole was well tolerated.

A 6-week open-label study with riluzole in treatment-resistant DSM-IV major (unipolar) depression (Protocol #02-M-0034) (Zarate et al., 2004). Patients received riluzole at a mean daily dose of 168.8 + 27.2 mg (84.2% took a dose of 150 mg/day or more) for a mean duration of 5.4 ± 3.7 weeks. Sixty-eight percent (N=13) of subjects completed the 6-week trial. The reasons for discontinuation were adverse events N=3 (1 increased liver function tests, 1 malaise, 1 nausea/vomiting), non-response N=2, and administrative N=1. The most common adverse events during the trial were headache (58%), gastrointestinal distress (nausea or vomiting) (43%), decreased salivation (47%), constipation (32%), and tension/inner unrest (26%); similar side effects have been observed with riluzole in ALS trials (Bensimon et al., 1994). No serious adverse events were noted. One subject was discontinued from the study because of an increase in liver function tests (LFTs) that was 3 times the upper normal limit. This subject was asymptomatic for hepatic dysfunction, and LFTs normalized shortly after discontinuing riluzole. There was no relationship between dose of riluzole and adverse events or changes in laboratory tests.

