Continuous monitoring of the participant's health while taking the assigned medication is performed by the Medical Monitor in conjunction with the Principal and Associate Investigators during the scheduled weekly visits. Participants will have clinical biochemistry laboratory blood assays performed to monitor their liver state and function. Liver Function Test (LFTs) will be run first at the Screening Visit and then weekly while taking the assigned medication. In the period between screening and randomization, the participant will be instructed not to begin taking study medication until the Investigator confirms that LFTs are within normal limits. Specifically, their alanine transaminase (ALT), aspartate transaminase (AST), total/direct bilirubin, and alkaline phosphate, will be monitored on a weekly basis during Study Period II to ensure that participants do not have liver function tests elevated over 3x normal ranges. If elevated LFTs are encountered, the test will be repeated, and if levels remain elevated at or above 3x upper limit of normal, the participants on the higher dose will have their dose reduced to 100mg per

day and participants on the low dose will be removed from the study. If a participant's LFTs ever exceed 5x upper limit of normal, the study drug will be discontinued and the subject will be withdrawn from the study.

Elevated LFTs of only 2xs level are not clinically uncommon and are often associated with any number of unrelated medical conditions or complications. A mild elevation in LFTs is quite often temporary in nature, and quickly reversible. Initial studies in riluzole established the 3x level as diagnostic for liver enzyme impairment or disruption to ensure that unrelated medical conditions and complications do not compromise the study while still ensuring the highest safeguarding of the participant.

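### No safety contact is scheduled after the exit visit and no end date is set for event or pregnancy reporting, although the plan states a possible fetal risk for at least one month after the last dose

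*Combined protocol and SAP*

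**What the plan says.** **Schedule (section 9.5).** The last column is V9, week 8. Adverse events are marked through V9, and the liver panel at screening and V1 to V9. The row "Thyroid function, HIV, HCG, hepatitis screen and urine drug screen" is marked at screening and V9 only. Footnote a says "Exit visit to be performed at Visit 9 or sooner if the patient is discontinued from the study", and the Phase II text says "Subjects will be assessed weekly from Visit 1 through Visit 9". The abbreviation list includes "F/U = Follow-up visit", but no such column appears. The reimbursement table in 13.3 also stops at Visit 9.

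**Pregnancy (section 12.6, rationale).** Women and men are advised to avoid conception for at least one month after the last dose. For women the text adds "Pregnancy within this time after the study drug is given may be a risk to an unborn baby". It also says "Female participants will be given a pregnancy test post-treatment", with no date.

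**Liver (section 14.2 a).** Tests run at screening and then weekly on study drug. "If elevated LFTs are encountered, the test will be repeated", with no time limit. If the level stays at or above 3x the upper limit of normal (ULN), participants on the higher dose are reduced and those on the lower dose are removed. Above 5x ULN the participant is withdrawn. In two earlier studies described in 14.1, "LFTs normalized shortly after discontinuing riluzole".

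**After exit.** Section 14.2 a says that observation may be recommended and that removed participants receive follow-up care as necessary. Those removed for worsening illness may continue care at the study sites for up to 90 days. Section 16.1 sets reporting deadlines for serious events and unanticipated problems, without an end date. Sections 13.7 (withdrawal) and 15.1 (data monitoring) refer to a Legacy Protocol that is not among the documents.

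**The concern.** The plan describes possible harms that extend past its last scheduled observation. It warns about conception in the month after dosing but plans no test, call or report at the end of that month. It requires raised liver tests to be repeated, but ties scheduled testing to time on drug. It draws reassurance from enzymes that normalized off drug in earlier studies, but schedules no off-drug value of its own.

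At stake is what the trial can report by arm: whether any pregnancy occurred in the stated risk period, whether an elevation first seen at week 8 was confirmed, and whether raised enzymes recovered in participants taken off the drug. The primary CAPS comparison is not affected.

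**Working it through.** **1. The plan's own figure.** The documents give no figure on this point. The only design calculation is the power in 11.2. With difference 9, SD 15, 50 per arm and alpha 0.05, the noncentrality is 9 / (15 × √(2/50)) = 3.0 on 98 df. Exact power is 0.8439 two-sided and 0.9090 one-sided, against 0.844 and 0.909 stated. It reproduces, and safety follow-up changes neither N nor power.

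**2. Coverage of the stated window.** Last scheduled safety assessment: V9, or earlier at discontinuation. Stated window: at least one month after the last dose. Scheduled follow-up after the exit visit: 0 days.

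**3. Pregnancy.** The only HCG marked after screening is at V9. It cannot detect a later conception, and it says nothing about male participants' partners. Section 16.1 does not list pregnancy as a reportable event. The documents give neither the number of women nor a pregnancy rate, so no expected count can be computed.

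**4. Liver, by situation.**
- Raised before V9, dose reduced, still on study: weekly draws continue, so there is no gap.
- First raised in the V9 blood: the value is recorded, but the required repeat has no scheduled time.
- Withdrawn for raised tests: the exit visit includes a liver panel, but its interval from the last dose is not stated and nothing is scheduled afterwards.

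**5. Scale of the exit-draw gap.**
- Earlier studies (14.1): 8 completers plus 6 discontinued = 14 (8/14 = 57%), and 13 plus 6 = 19 (13/19 = 68%). Stopped for liver tests at about 3x ULN or more: 2 + 1 = 3 of 33 = 9.1%, exact 95% CI 1.9% to 24.3%.
- Expected with such an elevation among 50 on riluzole: 50 × 3/33 = 4.5. With 47 to 55 per arm (158 consented less 40% or 30%), this is 4.3 to 5.0.
- On-treatment draws are V2 to V9, which is 8, and the exit draw is one of them. Assuming even onset, first raised at exit: 4.5 / 8 = 0.57. Over the CI, 50 × 0.0192 / 8 = 0.12 to 50 × 0.2433 / 8 = 1.5.
- Chance of at least one: 1 − (1 − 0.0909/8)^50 = 44%.
- Using instead the bound of 4% that 14.1 quotes for ALT above 5x ULN: 50 × 0.04 / 8 = 0.25, and the chance of at least one is 1 − (1 − 0.005)^50 = 22%.

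**The case against.** A reader might infer that all safety recording stops at exit and that exit-draw elevations go unrecorded. The text does not support either. V9 includes a liver panel, so the value is captured. Serious-event and unanticipated-problem reporting in 16.1 has no end date, and the repeat rule in 14.2 a has no cut-off at exit. Observation and follow-up care are offered. Not scheduled is not the same as not recorded.

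A reader might also take 4.5 of 50 as the number removed without a recovery value. That fails too. The earlier studies discontinued participants at about 3x ULN, whereas here those on the higher dose are reduced first and keep weekly panels. The rate also comes from two small open-label studies.

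The supplied text is incomplete as well. Withdrawal and data monitoring sit in the Legacy Protocol, which may fill the gap. The unused follow-up abbreviation is weak evidence, because the same list defines a washout phase with no column. Finally, the one-month window concerns conception, so using it for adverse events is a matter of convenience.

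These points narrow the concern but do not remove it. Section 15.2 sends safety monitoring to 14.2, which is supplied and sets no contact or data capture after exit. The observation is optional and of unstated length, the care is as needed, and neither is said to feed the trial data. Reporting without planned contact depends on the investigator happening to hear of an event, and it would not reliably capture pregnancies, non-serious events or enzyme recovery.

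**Conclusion.** The point holds in limited form. The plan schedules no safety contact after the exit visit and gives no end date for event or pregnancy reporting, while stating a possible fetal risk for at least one month after the last dose. Conceptions in that month, the repeat of an exit-draw elevation, and off-drug liver values in withdrawn participants may therefore not reach the trial data.

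The expected liver numbers are small: about 0.6 of 50 riluzole participants first raised at exit, or 0.25 using the 4% bound. Both rest on the assumptions that onsets are even over 8 draws and that the borrowed rates apply here. Pregnancies cannot be estimated. It cannot be excluded that the Legacy Protocol already covers part of this. The change is worth making because it is cheap and yields information that the plan as written would not reliably produce.

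**What to change.** - In 14.2 a and the schedule, add one telephone contact by existing staff about one month after the last dose, for completers and early exits alike. Record pregnancies (including partners') and adverse events, and state that this contact ends routine event and pregnancy recording.
- Enter in the trial database any repeat or follow-up liver test done under the repeat rule or the follow-up care in 14.2 a. Report exit-visit elevations by arm as confirmed, not confirmed or not repeated.
- Reconcile the schedule and its abbreviations, the undated post-treatment pregnancy test in 12.6, the repeat and after-care text in 14.2 a, and 16.1, with each other and with the Legacy Protocol. This concerns recording only; no dose or clinical rule is proposed.
- Use AHLTA/CHCS records (10.7) only where current authorization covers it. The identifier boxes in 10.9 are ticked only for non-MHS systems.

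**Cost.** A short amendment, participant agreement, and one call per participant. If each call takes the 10 minutes that the plan allows for its Phase I call (an assumption), 100 randomized participants need 100 × 10 / 60 = about 17 staff hours. No clinic visit is added, and sample size and power are unchanged.
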